7. PHARMACOKINETIC ANALYSES

7.1. Primary Pharmacokinetic Analyses

7.1.1. Endpoint / Variables

7.1.1.1. Drug Concentration Measures

Refer to [Appendix 3: Data Display Standards & Handling Conventions \(Section 10.3.3 Reporting Standards for Pharmacokinetic\)](#). Only total gepotidacin plasma PK concentrations will be measured and reported in the bioanalytical data. Therefore, unbound plasma PK concentrations will be derived by multiplying the total plasma PK concentrations by 0.67, to correct for the low plasma protein binding of gepotidacin (33%) observed in previous studies.

7.1.1.2. Derived Pharmacokinetic Parameters

Pharmacokinetic parameters will be calculated by standard non-compartmental analysis according to current working practices and using the currently supported version of WinNonlin (8.0 or higher). All calculations of non-compartmental parameters will be based on actual sampling times. Pharmacokinetic parameters listed will be determined from the plasma concentration-time data, as data permit.

Parameter	Parameter Description
AUC(0-t)	Area under the plasma concentration-time curve from time 0 (predose) to the last quantifiable concentration, to be calculated using the linear trapezoidal rule for each incremental trapezoid and the log trapezoidal rule for each decremental trapezoid.
AUC(0-∞)	Area under the concentration-time curve from time 0 (predose) extrapolated to infinite time, to be calculated using the linear trapezoidal rule for each incremental trapezoid and the log trapezoidal rule for each decremental trapezoid. (Calculated for single dose administration)
AUC(0-24)	Area under the plasma concentration-time curve from time 0 (predose) to the concentration at 24 hours postdose (post first dose for periods where 2 doses are administered), to be calculated using the linear trapezoidal rule for each incremental trapezoid and the log trapezoidal rule for each decremental trapezoid.
AUC(0-48)	Area under the plasma concentration-time curve from time 0 (predose) to the concentration at 48 hours postdose (post first dose for periods where 2 doses are administered), to be calculated using the linear trapezoidal rule for each incremental trapezoid and the log trapezoidal rule for each decremental trapezoid.
AUC(0-τ)	Area under the concentration-time curve from time 0 (predose) to time tau (tau = 12 and 6 for Part 1, Periods 2 and 3, respectively; for Part 2, tau will be between 6 and 12) (Calculated for periods where 2 doses are administered)
C _{max}	Maximum observed concentration, determined directly from the concentration-time data.
Ro AUC	Accumulation ratio calculated as AUC(0-τ) after the second dose, where 0 is the timepoint prior to second dose, divided by AUC(0-τ) after the first dose, where 0 is the predose timepoint prior to the first dose. (Calculated for periods where 2 doses are administered)
Ro C _{max}	Accumulation ratio calculated as C _{max} after the second dose divided by C _{max} after the first dose. (Calculated for periods where 2 doses are administered)

NOTES:

- Additional parameters may be included as required.

7.1.2. Summary Measure

Part 1

Pharmacokinetic parameters AUC(0- t), AUC(0-∞) (Period 1), AUC(0-24), AUC(0-48), AUC(0-τ) (Part 1 Periods 2 and 3), C_{max}, RO AUC (Part 1 Period 2 and 3), and RO C_{max} (Part 1 Period 2 and 3) following a single 1500 mg dose of gepotidacin (Part 1 Period 1) and two 3000 mg doses of gepotidacin (Part 1 Periods 2 and 3) in healthy adult participants will be summarized by treatment. Gepotidacin PK parameter estimates will be listed by participant and treatment.

Part 2

Pharmacokinetic parameters AUC(0- t), AUC(0-∞) (Part 2 Period 1), AUC(0-24), AUC(0-48), AUC(0-τ) (Part 2 Period 2), C_{max}, RO AUC (Part 2 Period 2), and RO C_{max} (Part 2 Period 2) following a single 1500 mg dose of gepotidacin (Part 2 Period 1) and two 3000 mg doses of gepotidacin at a time interval determined based on data from Part 1 (Part 2 Period 2) in healthy adolescent participants will be summarized by treatment. Gepotidacin PK parameter estimates will be listed by participant and treatment.

7.1.3. Population of Interest

The primary PK analyses will be based on the PK population for plasma PK concentrations and the PK parameter population for plasma PK parameters.

7.1.4. Statistical Analyses / Methods

Details of the planned displays are provided in Section 10: List of Data Displays and will be based on GSK Data Standards and statistical principles.

Unless otherwise specified, endpoints/ variables defined in Section 7.1.1 will be summarized using descriptive statistics, graphically presented (where appropriate) and listed.

Primary plasma PK parameters AUC(0- t), AUC(0-∞) (Period 1), AUC(0-24), AUC(0-48), AUC(0-τ) (Periods 2 and 3), C_{max}, RO AUC (Periods 2 and 3), and RO C_{max} (Periods 2 and 3) will be estimated for gepotidacin. For each of these parameters the following summary statistics will be calculated by Study Part and treatment: median, maximum, minimum, arithmetic mean, SD, 95% confidence interval (CI) for the arithmetic mean, geometric mean, CV on geometric mean, 95% CI for the geometric mean, and SD of logarithmically transformed data.

7.1.4.1. Statistical Methodology Specification

There are no planned statistical PK analyses additional to summary statistics.

7.2. Secondary Pharmacokinetic Analyses

7.2.1. Endpoint / Variables

7.2.1.1. Derived Pharmacokinetic Parameters

Pharmacokinetic parameters will be calculated by standard non-compartmental analysis according to current working practices and using the currently supported version of WinNonlin (8.0 or higher) or using the currently supported version of SAS (9.4 or higher). All calculations of non-compartmental parameters will be based on actual sampling times.

Plasma/urine pharmacokinetic parameters listed below will be determined from the plasma/urine concentration-time data, as data permit.

Parameter	Parameter Description
Ae total	Total unchanged drug (total amount of drug excreted in urine), calculated by adding all the fractions of drug collected over all the allotted time intervals
Ae(t1-t2)	Amount of drug excreted in urine in time intervals of predose, 0 to 2 hours, 2 to 4 hours, 4 to 6 hours, 6 to 8 hours, 8 to 12 hours, 12 to 24 hours, 24 to 36 hours, 36 to 48 hours, and 48 to 60 hours (Part 1, Period 2 and Period 3) after dosing
AUC(0-τ)	Area under the concentration-time curve from time 0 (predose) to time tau (tau = 12 and 6 for Part 1, Periods 2 and 3, respectively; for Part 2, tau will be between 6 and 12) (urine)
AUC(0-24)	Area under the concentration-time curve from time 0 (predose) to 24 hours postdose administration following the first dose (urine)
AUC(0-48)	Area under the concentration-time curve from time 0 (predose) to 48 hours postdose administration following the first dose (urine)
fe%	Percentage of the given dose of drug excreted in urine, calculated as: $fe\% = (Ae\ total/Dose) \times 100\%$
CLr	Renal clearance of drug, calculated as: $Ae\ total/AUC(0-t)$
Tmax	Time to reach maximum observed plasma concentration
tlag	Lag time before observation of drug concentrations in plasma
t1/2	Apparent terminal phase half-life (plasma)

NOTES:

- Additional parameters may be included as required.

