Participants will participate in 2 treatment periods and blood and urine samples will be collected for PK analysis of gepotidacin concentrations up to 48 hours after dosing.

Disclosure Statement: This is a sequential clinical pharmacology study that is masking the participant and investigator to assigned treatment.

Number of Participants: Approximately 17 adult participants will be randomly assigned to study intervention in Part 1 to ensure 12 evaluable participants on study drug with evaluable primary PK parameters and 2 participants on placebo with evaluable safety measurements. In Part 2, approximately 17 adolescent participants will be randomly assigned to study intervention to ensure 12 evaluable participants on study drug with evaluable primary PK parameters and 2 participants on placebo with evaluable safety measurements.

Intervention Groups and Duration: The treatments will be as follows:

Part 1 - Adult Participants

- Treatment A: Single dose 1500 mg (Period 1)
- Treatment B: Matching placebo (Period 1)
- Treatment C: Two 3000 mg doses given at Hour 0 and Hour 12 (Period 2)
- Treatment D: Two matching placebo doses given at Hour 0 and Hour 12 (Period 2)
- Treatment E: Two 3000 mg doses given at Hour 0 and Hour 6 (Period 3)
- Treatment F: Two matching placebo doses given at Hour 0 and Hour 6 (Period 3)

Note: All doses will be taken after a standard meal.

Part 2 - Adolescent Participants

- Treatment A: Single dose 1500 mg (Period 1)
- Treatment B: Matching placebo (Period 1)
- Treatment G: Two 3000 mg doses (Period 2; exact dosing interval to be determined after Part 1 is complete)
- Treatment H: Two matching placebo doses (Period 2; exact dosing interval to be determined after Part 1 is complete)

Note: All doses will be taken after a standard meal.

[figure not shown]
The duration of the study, including Screening, is approximately 47 days for Part 1, and 52 days for Part 2.

Data Monitoring Committee: No

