² Triplicate 12-lead ECGs will be measured at predose. Single 12-lead ECGs will be measured at all other time points.

³ Urine collection intervals include 0 (predose), 0 to 2 hours, 2 to 4 hours, 4 to 6 hours, 6 to 8 hours, 8 to 12 hours, 12 to 14 hours, 14 to 16 hours, 16 to 18 hours, 18 to 20 hours, 20 to 24 hours, 24 to 36 hours, 36 to 48 hours, and 48 to 60 hours.

Table 5 Safety and PK Assessments - Part 1, Period 3 (6-Hour Dose Interval, Adult Participants)

Procedure ¹	Treatment Period 3 Time point (hours)																									
	Predose	0	0.5	1	1.5	2	2.5	3	4	6	6.5	7	7.5	8	8.5	9	10	12	14	18	24	36	48	60		
12-lead ECG ²	X		X	X	X	X	X	X	X	X	X	X	X	X	X	X	X	X	X	X	X	X	X	X	X	
ECG Holter monitoring	X	X																								
Vital signs	X				X	X			X				X	X			X		X	X	X	X	X	X	X	
Study intervention		X								X																
Blood PK sample	X		X	X	X	X	X	X	X	X	X	X	X	X	X	X	X	X	X	X	X	X	X	X	X	X
Urine PK collection ³	X	X			X			X	X			X			X	X	X	X	X	X	X	X	X	X	X	

ECG = electrocardiogram; PK = pharmacokinetic.

¹ When coinciding with safety and/or PK assessments, ECGs, vital signs, and PK blood collections should be performed in said order.

² Triplicate 12-lead ECGs will be measured at predose. Single 12-lead ECGs will be measured at all other time points.

³ Urine collection intervals include 0 (predose), 0 to 2 hours, 2 to 4 hours, 4 to 6 hours, 6 to 8 hours, 8 to 10 hours, 10 to 12 hours, 12 to 14 hours, 14 to 18 hours, 18 to 24 hours, 24 to 36 hours, 36 to 48 hours, and 48 to 60 hours.

Table 6 Schedule of Activities - Part 2 (Adolescent Participants)

Procedure ¹	Check-in	Treatment Period 1 (Days)			Check-in ²	Treatment Period 2 (Days)			Follow-up (7 [±3] days after last dose) or Early Termination	Notes
	-1	1	2	3	-1	1	2	3		
Confined to clinic	X	X	X	X ³	X	X	X	X ³		Treatment Period 1 and Treatment Period 2 may be separated by 7 days but no more than 10 days.
Inclusion and exclusion criteria	X				X					Recheck clinical status before study intervention
Brief physical examination ⁴	X				X			X	X	
Pregnancy test	X				X				X	Urine pregnancy test (if WOCBP), as appropriate (see Table 10)
Drug, alcohol, and cotinine screen	X				X					See Table 10
Laboratory assessments	X			X	X			X	X	Including serum chemistry, hematology, and urinalysis (see Appendix 2)
12-lead ECG ⁵	X	X	X	X	X	X	X	X	X	See Table 7 , Table 8 , and Table 9 for timing of assessments
ECG Holter monitoring ⁶	X	X	X		X	X	X			See Table 7 , Table 8 , and Table 9 for timing of assessments

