³ Urine collection intervals include 0 (predose), 0 to 2 hours, 2 to 4 hours, 4 to 6 hours, 6 to 8 hours, 8 to 12 hours, 12 to 14 hours, 14 to 16 hours, 16 to 18 hours, 18 to 20 hours, 20 to 24 hours, 24 to 36 hours, and 36 to 48 hours.

Note: The number of PK samples and the PK sampling time points may be modified based on the adult PK data from Part 1.

- In Part 2, Period 2, the timing and number of planned study assessments, including safety, pharmacokinetic (PK), or other assessments may be altered during the course of the study based on data from Part 1 (e.g., to obtain data closer to the time of peak plasma concentrations) to ensure appropriate monitoring.
- Any changes in the timing or addition of time points for any planned study assessments as the result of emerging PK data from Part 1 must be documented and approved by the GlaxoSmithKline (GSK) study team and then archived in the sponsor and site study files, but will not constitute a protocol amendment. The Institutional Review Board (IRB)/Independent Ethics Committee (IEC) will be informed of any safety issues that constitute a substantial amendment and require alteration of the safety monitoring scheme or amendment of the informed consent form (ICF)/assent. The changes will be approved by the competent authorities (CA) and the ethics committee (EC) before implementation.

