² Triplicate 12-lead ECGs will be measured at predose. Single 12-lead ECGs will be measured at all other time points.

³ Urine collection intervals include 0 (predose), 0 to 2 hours, 2 to 4 hours, 4 to 6 hours, 6 to 8 hours, 8 to 10 hours, 10 to 12 hours, 12 to 14 hours, 14 to 18 hours, 18 to 24 hours, 24 to 36 hours, 36 to 48 hours, and 48 to 60 hours.

Note: The number of PK samples and the PK sampling time points may be modified based on the adult PK data from Part 1.

Table 9 Safety and PK Assessments - Part 2, Period 2 (if 12-hour dose interval is selected)

Procedure ¹	Treatment Period 2																										
	Time point (hours)																										
	Predose	0	0.5	1	1.5	2	2.5	3	4	6	8	12	12.5	13	13.5	14	14.5	15	16	18	20	24	36	48	60		
12-lead ECG ²			X	X	X	X	X	X	X	X	X	X	X	X	X	X	X	X	X	X	X	X	X	X	X	X	
ECG Holter monitoring	X									X																	
Vital signs					X	X			X		X	X			X	X					X		X	X	X	X	
Study intervention		X										X															
Blood PK sample	X		X	X	X	X	X	X	X	X	X	X	X	X	X	X	X	X	X	X	X	X	X	X	X	X	
Urine PK collection ³	X		X				X			X	X	X	X				X			X	X	X	X	X	X	X	X

ECG = electrocardiogram; PK = pharmacokinetic.

¹ When coinciding with safety and/or PK assessments, ECGs, vital signs, and PK blood collections should be performed in said order.

² Triplicate 12-lead ECGs will be measured at predose. Single 12-lead ECGs will be measured at all other time points.

³ Urine collection intervals include 0 (predose), 0 to 2 hours, 2 to 4 hours, 4 to 6 hours, 6 to 8 hours, 8 to 12 hours, 12 to 14 hours, 14 to 16 hours, 16 to 18 hours, 18 to 20 hours, 20 to 24 hours, 24 to 36 hours, 36 to 48 hours, and 48 to 60 hours.

Note: The number of PK samples and the PK sampling time points may be modified based on the adult PK data from Part 1.

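### In the two-dose periods, Ae total and fe% cover 0–60 h in adults but 0–48 h in adolescents under the protocol schedule, and the SAP's Part 2 tables conflict with that schedule

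*SAP*

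**What the plan says.** **Definitions (SAP 7.2.1.1; Protocol 9.4.1 has the same formulas).** Ae total is "calculated by adding all the fractions of drug collected over all the allotted time intervals". No end time is fixed. fe% is described as "Percentage of the given dose of drug excreted in urine, calculated as" Ae total over dose, times 100, so it takes whatever window Ae total has.

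**Adult two-dose periods (Protocol 1.3, Tables 4 and 5).** Urine is collected to 60 h in both. The Period 3 footnote ends "14 to 18 hours, 18 to 24 hours, 24 to 36 hours, 36 to 48 hours, and 48 to 60 hours", and the Period 2 footnote also ends with a 48–60 h interval.

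**Adolescent two-dose period.** The synopsis says for Part 2 that "blood and urine samples will be collected for PK analysis of gepotidacin concentrations up to 48 hours after dosing". Protocol Tables 8 and 9 agree. The Table 9 footnote ends "20 to 24 hours, 24 to 36 hours, and 36 to 48 hours", and a footnote to Table 6 allows discharge after the Hour 48 assessments.

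**SAP copy of the schedule (SAP 10.1.2).** Its Tables 8 and 9 for Part 2, Period 2 carry an Hour 60 column. The Table 9 footnote ends "20 to 24 hours, 24 to 36 hours, 36 to 48 hours, and 48 to 60 hours". SAP 7.2.1.1, however, assigns the 48–60 h urine interval to Part 1, Periods 2 and 3 only. The list of changes in SAP 2.1, as far as it can be read, mentions no change to Part 2 sampling.

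**The concern.** An endpoint defined as the sum of whatever was collected depends on the length of collection. In the two-dose periods the same label, fe%, would describe a longer collection in adults than in adolescents. The extra 12 h can only add drug to the adult total, so the difference runs one way. A true age difference with higher urinary recovery in adults would look the same in the headline figure.

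The study is meant to support including adolescents in Phase III (Protocol 2.1, 4.2), and urinary recovery is a secondary endpoint in both Parts, so readers are likely to set the two values side by side. Plasma has a remedy in AUC(0-48), timed from the first dose in both Parts. Urinary amount and fe% after two doses have no such counterpart. Urine AUC(0-48) is defined, but it is a concentration area and not an amount.

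The conflicting SAP tables add a practical problem: from the SAP alone a programmer cannot tell whether an adolescent 48–60 h interval exists.

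**Working it through.** **1. The plan's own precision figure, as a yardstick.** Protocol 9.2 gives the distance from the geometric mean to the upper 95% limit at n = 12 as 14.5% for AUC(0-∞) (CV 21.5%) and 28.0% for Cmax (CV 40.3%). The formula is exp[t(0.975, 11) × √ln(1 + CV²) / √12] − 1, with t = 2.201.

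- AUC: exp(2.201 × 0.2126 / 3.464) − 1 = 14.46%
- Cmax: exp(2.201 × 0.3879 / 3.464) − 1 = 27.95%

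Both reproduce. The window question does not depend on them, and they are plasma figures. They only give a sense of scale.

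**2. Windows under the protocol schedule.** Time after the second dose is the end of collection minus the dosing interval.

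| Interval | Adults, end 60 h | Adolescents, end 48 h |
|---|---|---|
| 12 h | 60 − 12 = 48 h | 48 − 12 = 36 h |
| 6 h | 60 − 6 = 54 h | 48 − 6 = 42 h |

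Under SAP Tables 8 and 9 both Parts would end at 60 h and the gap would vanish. In Period 1 both Parts end at 48 h (Protocol Tables 3 and 7), so single-dose Ae total and fe% are already matched.

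**3. Size.** The documents give no half-life, so it is assumed. The model is one compartment with linear kinetics, first-order absorption ka, two equal doses at 0 and τ, and urinary excretion proportional to elimination.

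- F(t) = 1 − [ka·exp(−kt) − k·exp(−ka·t)] / (ka − k), with k = ln 2 / half-life
- A(T) = F(T) + F(T − τ)
- Adult excess = A(60)/A(48) − 1

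Example with half-life 12 h, τ = 12 h, ka = 1.0 per h: k = 0.0578 and ka/(ka − k) = 1.0613. Then F(36) = 0.8673, F(48) = 0.9337 and F(60) = 0.9668. The excess is (0.9668 + 0.9337)/(0.9337 + 0.8673) − 1 = 5.5%.

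| Half-life (assumed) | τ = 12, ka 1.0 | τ = 12, ka 0.5 | τ = 6, ka 1.0 | τ = 6, ka 0.5 |
|---|---|---|---|---|
| 6 h | 0.84% | 0.96% | 0.50% | 0.58% |
| 8 h | 2.19% | 2.43% | 1.52% | 1.68% |
| 10 h | 3.84% | 4.17% | 2.88% | 3.12% |
| 12 h | 5.52% | 5.93% | 4.35% | 4.66% |

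Outside that range, a 4 h half-life gives about 0.1% and a 20 h half-life about 10–12%. If only 25% of exposure lies in a slow phase with a 12 h half-life, and the rest in a fast phase with a 2 h half-life, the excess falls to 1.20% (12 h interval) or 0.96% (6 h interval).

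**4. Can a common window be built from planned samples?** Yes. Every two-dose schedule has a urine boundary at 48 h, and the single-dose schedules end there.

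**The case against.** **No cross-Part urine comparison is planned.** SAP 7.1.4.1 and 7.2.4.1 plan summary statistics only, urine parameter Table 3.4 is paginated by Part, and no objective compares renal excretion between age groups. The adult–adolescent two-dose parameter figures (3.9 and 3.11) use Cmax and AUC(0-48). This stands, and it is why the point is minor.

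**The excess is visible.** The adult 48–60 h amount is itself a reported Ae(t1-t2) interval. A reader might infer that the window effect cannot be separated from an age effect, but the documents do not support that: the listed interval can be subtracted. What remains is that a summary of fe%(0-48), with its geometric mean and confidence interval, cannot be rebuilt from summaries of separate intervals.

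**Part 2 sampling may be modified.** The protocol allows changes based on Part 1 data, and the SAP's copy of the Part 2 schedule lacks the discharge-after-Hour-48 footnote, so a deliberate extension is conceivable. However, the SAP heads these tables as protocol-defined, still leaves the Part 2 interval undetermined, repeats modification as a future possibility, and in 7.2.1.1 keeps 48–60 h to Part 1. The conflict remains, and the mismatch depends on which text governs.

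**Two stronger readings are tempting.** One is that AUC(0-t) runs to 60 h in adults and 48 h in adolescents. It does not. It is the "Area under the plasma concentration-time curve from time 0 (predose) to the last quantifiable concentration", so its end varies by participant and only its ceiling differs. The other is that renal clearance carries the same bias as fe%. It is Ae total over AUC(0-t), so a longer collection lengthens numerator and denominator together and the effect largely cancels. A mismatch arises only where plasma becomes unquantifiable before the last urine interval. That is a separate question.

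**Conclusion.** The point holds for two endpoints in one setting: Ae total and fe% in the two-dose periods, under the protocol schedule. The difference in window follows from the text and needs no model. Its size does need one. For an assumed half-life of 6–12 h the adult excess is about 0.5–6%, and nearer 1% if only a quarter of exposure lies in the terminal phase. That is well inside the 14.5% precision distance planned for AUC(0-∞), but it is systematic and avoidable.

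The contradiction between SAP Tables 8 and 9 on one side and protocol Tables 8 and 9 and SAP 7.2.1.1 on the other is plain and must be reconciled. The documents do not settle which text governs. Overall this is a minor matter of definition and consistency. It does not threaten the primary plasma results.

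**What to change.** 1. In SAP 7.2.1.1, define Ae(0-48) and fe%(0-48), timed from the first dose, for every period in both Parts. Use them for any adult–adolescent statement on urinary recovery, comparing periods with the same dosing interval, because a common end time from the first dose equalises time after the second dose only then.
2. Keep Ae total and fe% to the end of collection as descriptive endpoints, and state the collection window next to each.
3. Reconcile the Hour 60 column and footnotes in SAP Tables 8 and 9 with protocol Tables 8 and 9 and with SAP 7.2.1.1.

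The 0–48 h endpoints work whichever way item 3 is settled. The cost is a few lines of SAP text and two derived variables from samples already planned. SAP 7.2.1.1 already allows additional parameters, and no extra sampling is needed.

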10.1.2. Protocol Defined Safety and PK Assessments

Table 4 Safety and PK Assessments - Part 1, Period 1

Procedure ¹	Treatment Period 1 Time point (hours)															
	Predose	0	0.5	1	1.5	2	2.5	3	4	6	8	12	24	36	48	
12-lead ECG ²	X		X	X	X	X	X	X	X	X	X	X	X	X	X	
ECG Holter monitoring	X	X														
Vital signs	X				X	X			X		X	X	X	X	X	
Study intervention		X														
Blood PK sample	X		X	X	X	X	X	X	X	X	X	X	X	X	X	
Urine PK collection ³	X	X				X				X	X	X	X	X	X	

ECG = electrocardiogram; PK = pharmacokinetic.

- When coinciding with safety and/or PK assessments, ECGs, vital signs, and PK blood collections should be performed in said order.
- Triplicate 12-lead ECGs will be measured at predose. Single 12-lead ECGs will be measured at all other time points.
- Urine collection intervals include 0 (predose), 0 to 2 hours, 2 to 4 hours, 4 to 6 hours, 6 to 8 hours, 8 to 12 hours, 12 to 24 hours, 24 to 36 hours, and 36 to 48 hours.

Table 5 Safety and PK Assessments - Part 1, Period 2 (12-Hour Dose Interval)

Procedure ¹	Treatment Period 2 Time point (hours)																								
	Predose	0	0.5	1	1.5	2	2.5	3	4	6	8	12	12.5	13	13.5	14	14.5	15	16	18	20	24	36	48	60
12-lead ECG ²	X		X	X	X	X	X	X	X	X	X	X	X	X	X	X	X	X	X	X	X	X	X	X	X
ECG Holter monitoring	X	X																							
Vital signs	X				X	X			X		X	X			X	X				X		X	X	X	X
Study intervention		X										X													
Blood PK sample	X		X	X	X	X	X	X	X	X	X	X	X	X	X	X	X	X	X	X	X	X	X	X	X
Urine PK collection ³	X	X				X				X	X	X	X				X				X	X	X	X	X

ECG = electrocardiogram; PK = pharmacokinetic.

- 1 When coinciding with safety and/or PK assessments, ECGs, vital signs, and PK blood collections should be performed in said order.
- 2 Triplicate 12-lead ECGs will be measured at predose. Single 12-lead ECGs will be measured at all other time points.
- 3 Urine collection intervals include 0 (predose), 0 to 2 hours, 2 to 4 hours, 4 to 6 hours, 6 to 8 hours, 8 to 12 hours, 12 to 14 hours, 14 to 16 hours, 16 to 18 hours, 18 to 20 hours, 20 to 24 hours, 24 to 36 hours, 36 to 48 hours, and 48 to 60 hours.

Table 6 Safety and PK Assessments - Part 1, Period 3 (6-Hour Dose Interval)

Procedure ¹	Treatment Period 3																								
	Predose	Time point (hours)																							
	0	0.5	1	1.5	2	2.5	3	4	6	6.5	7	7.5	8	8.5	9	10	12	14	18	24	36	48	60		
12-lead ECG ²	X		X	X	X	X	X	X	X	X	X	X	X	X	X	X	X	X	X	X	X	X	X	X	
ECG Holter monitoring	X	X																							
Vital signs	X				X	X			X				X	X			X		X	X	X	X	X	X	

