10.3.3. Reporting Standards for Pharmacokinetics

Pharmacokinetic Concentration Data	
PC Windows Non-Linear (WNL) File	PC WNL file (xpt format) for the non-compartmental analysis will be created according to SOP 314000(2.0). Note: Concentration values will be imputed as per GUI_51487
Descriptive Summary Statistics, Graphical Displays and Listings	Refer to IDSL PK Display Standards. Refer to IDSL Statistical Principle 6.06.1. For continuous data: 
 NQs at the beginning of a participant profile (i.e. before the first incidence of a measurable concentration) are deemed to be zero as it is assumed that in this circumstance no drug is yet measurable in the blood. For NQs at the end of the participant profile (i.e. after the last incidence of a measurable concentration); 
 for individual plots and pharmacokinetic analyses these are dropped (set to missing) as they do not provide any useful information (and can erroneously indicate that absolutely no drug is present) for summary statistics, these are set to 0 (to avoid skewing of the summary statistics) Individual NQs which fall between two measurable concentrations are set to missing (individual values of this nature are assumed to be an anomaly) If two or more NQ values occur in succession between measurable concentrations, the profile will be deemed to have terminated at the last measurable concentration prior to these NQs. For the purpose of individual participant plots, these NQs will be set to 0, and the subsequent measurable concentrations will be retained. For the derivation of pharmacokinetic parameters, these NQs and any subsequent measurable concentrations will be omitted (set to missing). Note: Concentration values will be imputed as per GUI_51487 for descriptive summary statistics/analysis and summarized graphical displays only.

Pharmacokinetic Parameter Data	
PK Parameter to be Derived by Programmer	The following plasma PK parameters will be derived by the Programmer: Ro Cmax, Ro AUC The following urine PK parameters will be derived by the Programmer: Ae total, Ae(t1-t2), Fe%, CLr
Descriptive Summary Statistics, Graphical Displays and Listings	N, n, arithmetic mean, 95% CI of arithmetic mean, geometric mean, 95% CI of geometric mean, SD, SD of logged data, CV (%), and between-subject geometric coefficient of variation (CVb (%)) will be reported. $CV_b (\%) = \sqrt{(\exp(SD^2) - 1) * 100}$ (SD = SD of Ln-Transformed data)

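### CLr divides urine recovery over the whole collection by a plasma AUC that stops at the last quantifiable sample, so it is overstated whenever plasma drops out first while drug is still being excreted.

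*SAP*

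**What the plan says.** CLr is a secondary endpoint in both Parts. Protocol 9.4.1 and SAP 7.2.1.1 agree on it: "Renal clearance of drug, calculated as" Ae total over AUC(0-t).

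- **Numerator.** Ae total is "calculated by adding all the fractions of drug collected over all the allotted time intervals" (SAP 7.2.1.1). For the single dose the last intervals are "8 to 12 hours, 12 to 24 hours, 24 to 36 hours, and 36 to 48 hours". For the two-dose periods of Part 1 they are "24 to 36 hours, 36 to 48 hours, and 48 to 60 hours" (SAP 10.1.2). For Part 2 Period 2 the SAP schedule runs to 60 h, but the protocol schedule stops at 48 h and SAP 7.2.1.1 reserves the 48 to 60 h interval for Part 1.
- **Denominator.** AUC(0-t) is the "Area under the plasma concentration-time curve from time 0 (predose) to the last quantifiable concentration" (SAP 7.1.1.2).
- **Non-quantifiable (NQ) values.** SAP 10.3.3 says of NQs at the end of a profile that "for individual plots and pharmacokinetic analyses these are dropped (set to missing) as they do not provide any useful information". If two or more NQs occur in succession between measurable values, the profile is taken to end before them. Later measurable plasma values are then left out of parameter derivation.

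Neither document restricts Ae total to the interval covered by AUC(0-t), and neither defines a CLr over matched intervals.

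**The concern.** Renal clearance as a ratio of amount to exposure is meaningful only when both terms cover the same time. Here the numerator's end is fixed by the urine schedule, and the denominator's end is set by assay sensitivity in each participant. Drug excreted after tlast counts in the numerator with no matching plasma exposure below it.

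SAP 7.2.4 summarises CLr by Study Part and treatment with a 95% CI for the geometric mean. That interval describes sampling variation and would not show a bias built into the definition.

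**Working it through.** **Inputs.** The formula, the two windows and the NQ rules are those set out above. The documents state no CLr value, no assay limit and no half-life, so there is no plan figure to reproduce. Every percentage below rests on assumed kinetics.

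**Algebra.** Let T be the end of urine collection. With constant renal clearance, Ae(0-T) = CLr × AUC(0-T). The plan's ratio is then

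CLr × AUC(0-T)/AUC(0-tlast) = CLr/(1-f),

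where f is the share of AUC(0-T) lying after tlast. The relative error is 1/(1-f) - 1. It is never negative from this cause, and it is zero when tlast = T.

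| f | 0.5% | 1% | 2% | 5% | 10% | 20% |
|---|---|---|---|---|---|---|
| CLr overstated by | 0.5% | 1.0% | 2.0% | 5.3% | 11.1% | 25% |

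**Size under an assumed biexponential oral model.** The assumptions are an absorption rate of 1.2/h, an initial half-life of 2 h, a terminal half-life of 6, 10 or 14 h, and a terminal coefficient of 2%, 5% or 15%. Dosing times and collection windows are those of Part 1.

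| Period | T | tlast | CLr overstated by | Level at tlast in the highest case |
|---|---|---|---|---|
| Single dose | 48 h | 36 h | 0.1% to 5.5% | 5.3% of Cmax |
| Single dose | 48 h | 24 h | 0.5% to 17.3% | 9.6% of Cmax |
| Two doses, 12 h apart | 60 h | 48 h | 0.1% to 4.2% | 6.9% of Cmax |
| Two doses, 12 h apart | 60 h | 36 h | 0.3% to 12.7% | 12.6% of Cmax |
| Two doses, 6 h apart | 60 h | 48 h | 0.04% to 3.4% | 5.1% of Cmax |
| Two doses, 6 h apart | 60 h | 36 h | 0.2% to 10.3% | 9.2% of Cmax |

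Among scenarios where the level at tlast was at most 1% of Cmax, the largest error was 2.0% (single dose, terminal half-life 10 h, coefficient 2%, tlast 24 h, level 0.93% of Cmax). In the rows tabulated, every error of 5% or more had a terminal half-life of 10 or 14 h and a level at tlast of about 3.5% of Cmax or higher.

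**An upper illustration.** Take mono-exponential decay, a single dose, T = 48 h and tlast = 24 h.

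- Half-life 6 h: (1 - 2^-8)/(1 - 2^-4) = 0.9961/0.9375 = 1.06, or +6%.
- Half-life 12 h: (1 - 2^-4)/(1 - 2^-2) = 0.9375/0.75 = 1.25, or +25%.

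In the 12 h case the 36 h level is 2^-3 = 12.5% of the starting level. For that sample to be NQ, the assay limit must lie above 12.5% of the starting level.

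**With matched windows.** Ae(0-t*)/AUC(0-t*) = CLr for any t*, so the error is zero. The late scheduled plasma times (12, 24, 36, 48 and, where used, 60 h) are also urine-interval boundaries, so a common endpoint exists.

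**The case against.** The strongest reply is that the windows match by design. In the protocol schedules, plasma and urine sampling end at the same nominal hour in every period. A mismatch needs an NQ final plasma sample, or a profile cut short by consecutive embedded NQs, with drug still being excreted. Nothing in the documents shows that this will happen. This stands, and it makes the error conditional. It does not make the ratio right in the profiles where the condition is met.

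Three stronger readings are tempting and are not supported:

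- **That CLr will generally be too high.** The error is zero when the last plasma sample is quantifiable and negligible when little drug is excreted after tlast. A missed urine fraction pushes CLr downward.
- **That an error near 25% should be expected.** The arithmetic is correct, but it needs an assay limit above about 12% of peak. Such an assay would also leave 2^-2 = 25% of AUC(0-∞), a primary endpoint, to extrapolation, which would be the larger problem.
- **That the rule will create a spurious dose or age difference in CLr.** With the same assay limit and similar kinetics, 1500 mg falls below quantification sooner than 3000 mg, so a difference is possible. Doubling the dose delays that point by only about one half-life, however, and any error common to both groups cancels in a comparison. The documents contain nothing from which to size it. The planned adult-adolescent box plots and body-weight scatter plots use Cmax and AUC, not CLr (SAP 10.10.8).

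It is also true that little depends on CLr. No hypothesis is tested, the secondary PK analysis is summary statistics only (SAP 7.2.4.1), and the Part 2 dosing interval is chosen on plasma PK and safety. Since interval Ae values are derived and SAP 7.2.1.1 allows additional parameters, a matched CLr could be added at reporting. These points limit the importance. A definition fixed beforehand is still preferable to a parameter added once results are seen.

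**Conclusion.** Wrong as written, but minor. The upward direction follows from the plan's own definitions and needs only constant renal clearance. The size cannot be derived from the documents. On the assumed models it is about 2% or less if the last quantifiable level is at most 1% of Cmax. It reaches roughly 5% to 25% only with an insensitive assay or a long half-life. It affects only participants whose tlast precedes the end of urine collection while drug is still being excreted. A dose- or age-related difference in CLr remains a possibility and not a finding.

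**What to change.** Replace the definition in SAP 7.2.1.1 with CLr = Ae(0-t*)/AUC(0-t*), where t* is the last urine-interval boundary at or before plasma tlast and all urine intervals up to t* were collected. The second condition also guards against the downward error from a missed fraction. Record the change in SAP 2.1, because the protocol carries the same formula. Selecting t* on nominal times would prevent a plasma draw a few minutes early from pulling it back a whole interval.

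A fixed 48 h window is not an adequate substitute. SAP 7.1.1.2 takes AUC(0-48) to the concentration at 48 h. After the single dose, if that value is quantifiable the fixed window changes nothing (on nominal times). If it is NQ, AUC(0-48) is unavailable or needs an extrapolation that the SAP does not specify. In the Part 1 two-dose periods it would also discard the 48 to 60 h data.

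The cost is one line of text and a small programming change, using interval Ae values and plasma data already available. The downside is that CLr uses slightly less urine data in profiles where tlast is early. Ae total and fe% can stay as defined.
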